5.2. Key Secondary Efficacy Endpoints

The key secondary efficacy endpoints of this study are:

- Proportion of patients with disease progression on Day 28. Disease progression is defined as the
 proportion of patients who are not alive or who have respiratory failure. Respiratory failure is defined
 as patients who have a score of 2, 3 or 4 on the NIAID 8-point ordinal scale (see below).
- Proportion of patients with disease resolution on Day 28. Disease resolution is defined as patients who are alive and have a score of 6, 7, or 8 on the NIAID 8-point ordinal scale.
- All-cause mortality rate at Day 28
- Change of clinical status related to COVID-19 on Day 28 compared with baseline according to the following NIAID 8-point ordinal scale:
 - 1. Death
 - Hospitalized, on invasive ventilation (mechanical ventilator and/or Extracorporeal Membrane Oxygenation ECMO)
 - 3. Hospitalized, on non-invasive ventilation or high-flow oxygen devices
 - 4. Hospitalized, requiring supplemental oxygen
 - Hospitalized, not requiring supplemental oxygen, but requiring ongoing medical care (COVID-19 related or otherwise)
 - Hospitalized, not requiring supplemental oxygen and no longer requires ongoing medical care (used if hospitalization was extended for infection-control reasons)
 - 7. Not hospitalized, limitation on activities, and/or requiring home oxygen
 - 8. Not hospitalized, no limitations on activities

Please note: Patients requiring oxygen before COVID-19 and returning to baseline oxygen use will be considered improved (ie, not requiring supplemental oxygen). Patients with a limitation on activities before COVID-19 and returning to baseline activity will be considered improved. In case of death before Day 14 or Day 28, the patient will be considered with the NIAID score for death (score of 1) on the date of death in the analysis.

5.3. Other Secondary Efficacy Endpoints

The other secondary efficacy endpoints of this study are:

This document is confidential.

SAP Text Version: 2.0, 31-Aug-2022 Controlled Document ID: CCC , Effective Date 31-Aug-2020 Filing requirements: TMF

Page 23 of 56

- Proportion of patients with disease resolution on Day 14. Disease resolution is defined as patients who are alive and have a score of 6, 7, or 8 on the NIAID 8-point ordinal scale (as listed above).
- All-cause mortality rate at Day 14 and Day 60
- Change of clinical status related to COVID-19 on Day 14 compared with baseline according to the NIAID 8-point ordinal scale (as listed above)
- Proportion of patients requiring invasive ventilation (mechanical ventilator and/or ECMO), or who
 are not alive on Day 14 or Day 28
- · Proportion of patients in each category of the NIAID 8-point ordinal scale
- Time to (first) improvement of at least 1 category on the NIAID 8-point ordinal scale (until Day 28).
 Patients who did not improve at least 1 category on the NIAID scale or deaths before Day 28 will be censored at Day 28.
- The odds ratio between MP1032 and SoC and placebo and SoC of the number of patients with clinical status improvement from baseline on the NIAID 8-point ordinal scale (ie, an improvement of at least 1 category) at Day 14 and Day 28
- Total duration of hospitalization (from baseline to discharge; with death censored on the last day of the observed period – at Day 28 or Day 60, respectively)
- Proportion of patients alive and testing negative for COVID-19 on Day 14, Day 28 and Day 60

5.4. Exploratory Efficacy Endpoints

Exploratory efficacy endpoints of this study are:

- Change in saturation of oxygen (SpO₂)/fraction of inspired oxygen (FiO₂) ratio (for patients alive) on Day 14 or Day 28 compared with baseline
- Total number of days in the intensive care unit (ICU)
- Duration of invasive mechanical ventilation and/or ECMO
- Time to recovery from COVID-19 symptoms (stuffy or runny nose, sore throat, red or irritated eyes, shortness of breath, cough, low energy or tiredness, muscle or body aches, headache, chills or shivering, feeling hot or feverish, nausea, and number of times of vomit, times of diarrhea, sense of smell, sense of taste in the last 24 hours) at Day 14, Day 28, and Day 60
- Change from discharge in the EuroQol (EQ) index value and EQ visual analog scale (VAS) based on the EuroQol-5D-5L (EQ-5D-5L) questionnaire at Day 60

5.5. Pharmacokinetic Endpoints

 MP1032 plasma concentrations and PK parameters (if possible) including maximum observed plasma concentration, area under the concentration-time curve, elimination parameters, apparent body clearance, apparent volume of distribution, trough concentration, average observed plasma concentration at steady state, and other relevant PK parameters assessed via MP1032 plasma exposure on Day 1 and Day 7 in a PK subset of patients.

5.6. Pharmacodynamic Endpoints

Change from baseline in biomarker levels potentially including, but not limited to, cytokines (eg, C-reactive protein, interleukin [IL]-1β, IL-6, tumor necrosis factor-α, and IFN-γ), and other coagulation/inflammatory biomarkers (eg, D-dimer and ferritin)

This document is confidential.

SAP Text Version: 2.0, 31-Aug-2022 Controlled Document ID: CC , Effective Date 31-Aug-2020 Filing requirements: TMF

Page 24 of 56

5.7. Safety Endpoints

- Safety and tolerability assessed by:
 - Cumulative incidence of treatment-emergent AEs (summarized by seriousness, severity, relationship to the study medication, outcome, and duration)
 - Vital sign parameters
 - o Clinical laboratory parameters
 - Physical examination findings

This document is confidential.

Page 25 of 56

6. Analysis Sets

6.1. Screened / Randomized Set

The Screened Set will include all patients who give informed consent and are screened. Unless specified otherwise, this set will be used for summaries of patient disposition.

The Randomized Set will include all patients randomized. Unless specified otherwise, this set will be used for all patient listings with exception of the listing presenting screening failures and the respective reason(s) for screen failure.

6.2. Safety Set

The Safety Set (SS) will include all randomized patients who receive at least 1 dose of study drug. The treatment group assignment in the SS will be defined by the treatment actually received. The SS will be used for the analysis of safety.

6.3. Intention-To-Treat Set

The Intention-To-Treat Set (ITT) corresponds with the randomized set and will include all randomized patients, irrespective of any deviation from the protocol or premature discontinuation from study drug or withdrawal from study. The treatment group assignment will be designated according to initial randomization. The ITT will serve as the basis for the analysis of efficacy and summary of demographics and baseline characteristics.

6.4. Per Protocol Set

The Per Protocol Set (PPS) will include all patients from ITT who received at least 1 dose of study drug and who do not have any major protocol deviations affecting the efficacy assessments. Patients will be analyzed according to randomized treatment. The PPS will be used for supportive analyses of efficacy.

The final identification and categorization of all protocol deviations and the final definition of the analysis populations including the PPS will be performed in the Blind Data Review Meeting (BDRM) prior to database lock (following Syneos Health SOP 3911).

6.5. Pharmacokinetic Analysis Set

The Pharmacokinetic analysis set (PKS) will include all the patients who have been administered active study drug and have at least 1 postdose evaluable plasma concentration after Day 1 dose.

6.6. Protocol Deviations

Protocol deviations will be identified periodically throughout the trial following the 'Protocol Deviation and Non-compliance Management Plan' (Syneos Health SOP and WI, 3101 and 3101.W02). Final definition of protocol deviations and categorization into minor / major will be performed in the BDRM prior to database lock and unblinding.

All protocol deviations related to study inclusion or exclusion criteria, conduct of the trial, patient management, dosing, and sampling procedures or patient assessment will be listed. The list of protocol deviations will be reviewed by the Sponsor, the principal investigator and the study statistician, and finalized before database lock during the BDRM. Also the determination whether a major protocol deviation has an impact on the assessment of the primary efficacy, and the determination of the patient sets will be finalized in the BDRM following SOP 3911.

This document is confidential.

SAP Text Version: 2.0, 31-Aug-2022 Controlled Document ID: CC , Effective Date 31-Aug-2020 Filing requirements: TMF

Page 26 of 56

7. Estimands

7.1. Primary Efficacy Endpoint

The main estimand for the primary efficacy endpoint is defined as follows:

- Treatment: 300 mg MP1032 BID plus SoC in Arm A and placebo BID plus SoC in Arm B. If a patient terminates the study treatment, but still remains in the study and is followed up, then the patient will continue to receive either SoC alone or SoC+additional treatment. These treatments are defined with regards to intercurrent events as 'other treatments'.
- Population: Of all patients defined by the study inclusion / exclusion criteria, the analysis population will include all randomized patients (ITT population).
- Variable: A binary variable indicating disease progression (respiratory failure) when having completed Day 14 assessment or died prior to Day 14. Respiratory failure is defined as patients who have a score of 2, 3 or 4 on the NIAID 8-point ordinal scale.
- Intercurrent events: All events leading to study treatment discontinuation and/or switch to other treatment prior to Day 14 will be handled using the treatment-policy strategy (ie, the observed NIAID score at Day 14 will be used for definition of the failure in such patients).
- Population-level summary: Common risk difference resulting from the Mantel-Haenszel (MH) test
 considering the 4 strata out of the combinations of the 2 randomization stratification factors disease
 severity (moderate versus severe) and age-class (<65 years versus >65 years) at baseline.

Missing data on Day 14 resulting from study termination prior to Day 14 are not expected. However, in case it happens, such monotone missings will be imputed by multiple imputation using information from similar patients of the same treatment group assuming 'missing at random' (MAR) mechanism. Missing postbaseline data for patients randomized but not treated will be imputed by the respective baseline value (baseline observation carried forward, BOCF). Intermediate missing data of Day 14 (ie, NIAID assessments prior Day 14 and at Day 28 are available, but only Day 14 is missing) will be imputed by Last-observationcarried-forward (LOCF). The comparison between the treatment groups will be performed on the ITT after imputation of missing values using MH test for common risk difference considering the 4 strata resulting from the 2 randomization stratification factors disease severity (moderate versus severe) and age-class (≤65 years versus >65 years). 95% confidence interval (CI) will be provided for the risk difference.

A second estimand for the primary efficacy endpoint will be defined similar to the main estimand but with the only difference that the intercurrent event study drug discontinuation due to AE or due to lack of efficacy will be treated using the composite strategy as 'disease progression', but the intercurrent event of study drug discontinuation due to other reasons will be still treated with the treatment-policy strategy. The imputation strategy as described for the main estimand will be used for the second estimand also. Similar sensitivity analyses as for the main estimand will be applied for the second estimand.

7.2. Key Secondary Efficacy Endpoint 1

The main estimand for the key secondary efficacy endpoint 1 is defined as follows:

- Treatment: 300 mg MP1032 BID plus SoC in Arm A and placebo BID plus SoC in Arm B. If a patient
 terminates the study treatment, but still remains in the study and is followed up, then the patient
 will continue to receive either SoC alone or SoC+additional treatment. These treatments are
 defined with regards to intercurrent events as 'other treatments'.
- Population: Of all patients defined by the study inclusion / exclusion criteria, the analysis population will include all randomized patients (ITT population).

This document is confidential.

SAP Text Version: 2.0, 31-Aug-2022 Controlled Document ID: COMPANY, Effective Date 31-Aug-2020 Filing requirements: TMF

Page 27 of 56

- Variable: A binary variable indicating disease progression (respiratory failure) when having completed Day 28 assessment or died prior to Day 28. Respiratory failure is defined as patients who have a score of 2, 3 or 4 on the NIAID 8-point ordinal scale
- Intercurrent events: All events leading to study treatment discontinuation and/or switch to other treatment prior to Day 28 will be handled using the treatment-policy strategy (ie, the observed NIAID score at Day 28 will be used for definition of the failure in such patients).
- Population-level summary: Common risk difference resulting from the MH test considering the 4 strata out of the combinations of the 2 randomization stratification factors disease severity (moderate versus severe) and age-class (<65 years versus >65 years).

Missing data on Day 28 resulting from study termination prior to Day 28 (monotone missings) will be imputed by multiple imputation using information from similar patients of the same treatment group assuming 'MAR mechanism. Missing post-baseline data for patients randomized but not treated will be imputed by BOCF. The confirmatory comparison between the treatment groups will be performed on the ITT after imputation of missing values using MH test for common risk difference considering the 4 strata resulting from the 2 randomization stratification factors disease severity (moderate versus severe) and age-class (<65 years versus >65 years). 95% confidence interval (CI) will be provided for the risk difference.

A second estimand for the first key secondary efficacy will be defined similar to the main estimand but with the only difference that the intercurrent event study drug discontinuation due to AE or due to lack of efficacy will be treated using the composite strategy as 'disease progression', but the intercurrent event of study drug discontinuation due to other reasons will be still treated with the treatment-policy strategy. The imputation strategy as described for the main estimand will be used for the second estimand also. Similar sensitivity analyses as for the main estimand will be applied for the second estimand.

7.3. Key Secondary Efficacy Endpoint 2

The main estimand for the key secondary efficacy endpoint 2 is defined as follows:

- Treatment: 300 mg MP1032 BID plus SoC in Arm A and placebo BID plus SoC in Arm B. If a patient
 terminates the study treatment, but still remains in the study and is followed up, then the patient
 will continue to receive either SoC alone or SoC+additional treatment. These treatments are
 defined with regards to intercurrent events as 'other treatments'.
- Population: Of all patients defined by the study inclusion / exclusion criteria, the analysis population will include all randomized patients (ITT population).
- Variable: A binary variable indicating 'disease resolution' when having completed Day 28 assessment. Disease resolution is defined as patients who are alive and have a score of 6, 7, or 8 on the NIAID 8-point ordinal scale.
- Intercurrent events: All events leading to study treatment discontinuation and/or switch to other treatment prior to Day 28 will be handled using the treatment-policy strategy (ie, the observed NIAID score at Day 28 will be used for definition of the disease resolution in such patients). Death prior to Day 28 will be considered as non-resolution of disease (or failure) using the composite strategy.
- Population-level summary: Common risk difference resulting from the MH test considering the 4 strata out of the combinations of the 2 randomization stratification factors disease severity (moderate versus severe) and age-class (≤65 years versus >65 years).

Missing data on Day 28 resulting from study termination prior to Day 28 (monotone missings) will be imputed by multiple imputation using information from similar patients of the same treatment group assuming 'MAR mechanism. Missing post-baseline data for patients randomized but not treated will be imputed by BOCF. The confirmatory comparison between the treatment groups will be performed on the

This document is confidential.

SAP Text Version: 2.0, 31-Aug-2022 Controlled Document ID: CCI , Effective Date 31-Aug-2020 Filing requirements: TMF

Page 28 of 56

ITT after imputation of missing values using MH test for common risk difference considering the 4 strata resulting from the 2 randomization stratification factors disease severity (moderate versus severe) and ageclass (<65 years versus >65 years). 95% confidence interval (CI) will be provided for the risk difference.

A second estimand for the second key secondary efficacy endpoint will be defined similar to the main estimand but with the only difference that the intercurrent event study drug discontinuation due to AE or due to lack of efficacy will be treated using the composite strategy as 'non-resolution of disease (or failure)', but the intercurrent event of study drug discontinuation due to other reasons will be still treated with the treatment-policy strategy. The imputation strategy as described for the main estimand will be used for the second estimand also. Similar sensitivity analyses as for the main estimand will be applied for the second estimand.

7.4. Key Secondary Efficacy Endpoint 3

The main estimand for the key secondary efficacy endpoint 3 is defined as follows:

- Treatment: 300 mg MP1032 BID plus SoC in Arm A and placebo BID plus SoC in Arm B. If a patient
 terminates the study treatment, but still remains in the study and is followed up, then the patient
 will continue to receive either SoC alone or SoC+additional treatment. These treatments are
 defined with regards to intercurrent events as 'other treatments'.
- Population: Of all patients defined by the study inclusion / exclusion criteria, the analysis population will include all randomized patients (ITT population).
- Variable: A binary variable indicating life status (death due to any reason or alive) at Day 28.
- Intercurrent events: All events leading to study treatment discontinuation and/or switch to other treatment prior to Day 28 will be handled using the treatment-policy strategy (ie, the life status at Day 28 will be used in such patients).
- Population-level summary: Common risk difference of the all-cause mortality rate resulting from the MH test considering the 4 strata out of the combinations of the 2 randomization stratification factors disease severity (moderate versus severe) and age-class (≤65 years versus >65 years).

Missing data of the life status at Day 28 resulting from study termination prior to Day 28 are not expected. However, in case they happen, such missings will be imputed by death. The confirmatory comparison between the treatment groups will be performed on the ITT after imputation of missing values using MH test for common risk difference considering the 4 strata resulting from the 2 randomization stratification factors disease severity (moderate versus severe) and age-class (≤ 65 years versus ≥ 65 years). 95% confidence interval (CI) will be provided for the risk difference.

7.5. Key Secondary Efficacy Endpoint 4

The main estimand for the key secondary efficacy endpoint 4 is defined as follows:

- Population: Of all patients defined by the study inclusion / exclusion criteria, the analysis population will include all randomized patients (ITT population).
- Variable: Clinical status related to COVID-19 measured on the NIAID 8-point ordinal scale on Day 28 compared to the baseline assessment, ie, change from baseline of NIAID score.
- Intercurrent events: All events leading to study treatment discontinuation and/or switch to other treatment prior to Day 28 will be handled using the treatment-policy strategy (ie, the NIAID score at Day 28 will be used for such patients).
- Population-level summary: Risk difference between the treatment groups of the changes from baseline in the NIAID score as assessed in the ANCOVA model with the 2 randomization

This document is confidential.

Page 29 of 56

stratification factors disease severity (moderate versus severe) and age-class (≤65 years versus >65 years) as independent variables additionally to the treatment variable, and the baseline value of the NIAID score as covariate.

Missing data on Day 28 resulting from study termination prior to Day 28 will be imputed by multiple imputation using information from similar patients of the same treatment group assuming MAR mechanism. Missing post-baseline data for patients randomized but not treated will be imputed by BOCF. The confirmatory comparison between the treatment groups will be performed on the ITT after imputation of missing values using the ANCOVA model considering the 2 randomization stratification factors disease severity (moderate versus severe) and age-class (<65 years versus <65 years) as independent variables and the baseline assessment of NIAID as covariate. 95% confidence interval (CI) will be provided for the risk difference.

This document is confidential.

Page 30 of 56

8. General Aspects for Statistical Analysis

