- p. To standardize the assessment of COVID-19 severity, respiratory rate, SpO₂, and heart rate will be measured when the patient is on room air at sea level (ie, no supplemental oxygen, if possible) and at rest for at least 5 minutes. If possible, the site should collect the information from each patient at the same time each day (±1 hour).
- q. Record the patient's clinical status related to COVID-19 on the NIAID 8-point ordinal scale and also record the date and time for each individual component of the NIAID 8-point ordinal scale including: invasive or non-invasive mechanical ventilation/ECMO start/stop, high-flow/mask oxygen start/stop, supplemental oxygen start/stop (nasal cannula, liter flow [and its conversion to FiO₂], other delivery services), hospital discharge (whether with limitations or without limitations), hospitalization type (eg, transfer to ICU) start/stop, and (if applicable) death, cause of death (including relatedness to COVID-19), and date/time of death. If possible, the site should collect the information from each patient at the same time each day (±1 hour).
- r. The EQ-5D-5L (Appendix 2 of protocol) is only required for discharged patients and at the following visits: day of discharge, Day 60, and Early Termination visit (if applicable). The EQ-5D-5L is not required for patients who remain hospitalized until study end.
- s. The limited physical examination and clinical laboratory assessments on Day 8 (± 3 days) will be collected in all patients who remain hospitalized. If the patient is discharged before Day 8 (± 3 days), the site should arrange to have the physician assess the patient via a telephone/virtual call. If the physician determines during the telephone/virtual call that the limited physical examination and clinical laboratory assessments are clinically indicated, then the site should arrange for an outpatient visit to collect these assessments.

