10.1. Primary Efficacy Estimands and Analysis

The main estimand and the second estimand for the primary efficacy endpoint that is defined as a binary variable indicating disease progression (death or respiratory failure) at Day 14 will be compared between the treatment groups based on the common risk difference resulting from the MH test considering the 4 strata out of the combinations of the 2 randomization stratification factors disease severity (moderate versus severe) and age-class (\leq 65 years versus >65 years).

Missing data on Day 14 resulting from study termination prior to Day 14 are not expected. However, in case they happen, such monotone missings will be imputed by multiple imputation using information from similar patients of the same treatment group assuming the missings are MAR. Missing post-baseline data for patients randomized but not treated will be imputed by BOCF. Intermediate missing data of Day 14 (ie, NIAID assessments prior Day 14 and at Day 28 are available, but only Day 14 is missing) will be imputed by LOCF. The comparison between the treatment groups will be performed on the ITT after imputation of missing values using the MH test. 95% confidence interval (CI) will be performed by imputation of missing values at Day 14 with 'progression' assuming that missings happen not at random (MNAR). A table with number and type/reason of missing values in the primary efficacy variable will be provided by treatment group on the ITT.

All above described analyses will be repeated on PPS as supportive analysis. Additionally a logistic regression model with treatment and the 2 stratification factors as covariables will be applied on the ITT as supportive analysis.

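### An isolated missing Day 14 NIAID score is filled by LOCF without first consulting the dated clinical records, which, where complete, show whether the patient met the binary primary outcome

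*SAP*

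**What the plan says.** **Imputation rule.** SAP Section 7.1 describes the gap as "Intermediate missing data of Day 14 (ie, NIAID assessments prior Day 14 and at Day 28 are available" and continues "but only Day 14 is missing) will be imputed by Last-observationcarried-forward (LOCF". Section 10.1 repeats the rule for the analysis: "but only Day 14 is missing) will be imputed by LOCF". Early terminations before Day 14 are treated differently, by multiple imputation under missing at random. Patients randomized but never treated keep their baseline value.

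**Dated records.** Footnote q to Table 1 (Section 4.6) tells sites to enter the score and "also record the date and time for each individual component of the NIAID 8-point ordinal scale including: invasive or non-invasive mechanical ventilation/ECMO start/stop", then "high-flow/mask oxygen start/stop, supplemental oxygen start/stop", then "hospital discharge (whether with limitations or without limitations), hospitalization type (eg, transfer to ICU) start/stop", and the date and time of death.

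**Outcome.** Progression is death or respiratory failure, and Section 7.1 states: "Respiratory failure is defined as patients who have a score of 2, 3 or 4 on the NIAID 8-point ordinal scale". The primary variable therefore needs only the split 1-4 versus 5-8.

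**Safeguards already planned.** Section 10.1 includes an analysis that counts missing Day 14 values as progression, and a table of missing values by number, type or reason, and arm.

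**The concern.** The main estimand in Section 7.1 targets status on Day 14. If a patient's oxygen, ventilation, hospital and vital status on that day are on record, an older score is a substitute for information the trial already holds. LOCF also enters that score as certain, whereas early terminations in the same paragraph receive multiple imputation and its added uncertainty. The Day 28 score, which must exist for the rule to apply, plays no part in the imputed value.

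The exposed group is discharged patients. Table 1 schedules the NIAID score on Days 2 to 13, but Section 4.1 says patients are assessed while in hospital and that visits after discharge begin at Day 14. The last score may therefore be a 7 or 8 from the day of discharge. If such a patient is readmitted, is on oxygen on Day 14 and has no score entered, LOCF records no progression even where the dates show otherwise. Readmission is foreseen: Section 13.1 compares re-hospitalization rates between arms.

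**Working it through.** **1. Do the dated items fix the binary outcome?** Using the scale in Section 5.2:
- Category 1: date of death.
- Category 2: in hospital, with invasive ventilation/ECMO start and stop.
- Category 3: in hospital, with non-invasive ventilation or high-flow start and stop.
- Category 4: in hospital, with supplemental oxygen start and stop.
- Categories 5 and 6: in hospital, with none of these supports running.
- Categories 7 and 8: not in hospital.

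The split 1-4 versus 5-8 thus needs vital status, hospital status and respiratory support on Day 14, all of which footnote q asks to be dated. Hospital status cannot be skipped, because home oxygen falls in category 7. The Section 5.2 note on oxygen use before COVID-19 must also be applied. The dates do not clearly separate 5 from 6 (need for ongoing care) or 7 from 8 (limitation is recorded at discharge).

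**2. Does any step use them?** Sections 7.1, 8.3 and 10.1 contain no such derivation. Section 8.1 also keeps data from unscheduled visits out of the analyses, except COVID-19 tests.

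**3. The plan's own figure.** Inputs from Section 4.3: 10% versus 30%, two-sided alpha 10%, 76 + 38 patients.
- Pooled rate = (38 × 0.30 + 76 × 0.10)/114 = 0.1667.
- Null SE = √[0.1667 × 0.8333 × (1/38 + 1/76)] = 0.0740.
- Alternative SE = √[0.30 × 0.70/38 + 0.10 × 0.90/76] = 0.0819.
- z = (0.20 − 1.645 × 0.0740)/0.0819 = 0.955, so power is 83.0%, which reproduces the stated 83%.
- With 80 + 40 patients the same formula gives 84.6%.

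**4. One miscoded patient.** Arm A: 1/80 = 1.25 points. Arm B: 1/40 = 2.5 points.

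**5. Range under assumptions.** The SAP gives neither the rate of isolated gaps, m, nor the share of LOCF values on the wrong side of the cut, e; both are assumed here. Let f = m × e. With errors in both directions and equally in both arms, a true rate p becomes p(1 − f) + (1 − p)f, and the 20-point difference becomes 20 × (1 − 2f).

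| m | e | f | Difference (points) | Power, 80 + 40 |
|---|---|---|---|---|
| 2% | 10% | 0.002 | 19.92 | 84.2% |
| 2% | 30% | 0.006 | 19.76 | 83.4% |
| 5% | 10% | 0.005 | 19.80 | 83.6% |
| 5% | 30% | 0.015 | 19.40 | 81.5% |
| 10% | 10% | 0.010 | 19.60 | 82.5% |
| 10% | 30% | 0.030 | 18.80 | 78.2% |

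If LOCF errs only towards progression, power runs from 84.3% to 79.7%. If it errs only towards non-progression, it runs from 84.5% to 83.4%. For scale, m = 2% is 2.4 of 120 patients and m = 10% is 12.

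**The case against.** The case for leaving the rule alone has real weight.

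- **Inpatient scores are recent.** With scoring scheduled on Days 2 to 13, a reader might picture an inpatient scored 5 on Day 12 who starts oxygen on Day 13 and is then coded as not progressing. That does not follow: a Day 13 score is due, and if it is 4, LOCF carries progression. The example needs Day 13 to be missing too, or scored before oxygen began. This stands.
- **Gaps should be few.** The Day 14 visit has a ±2 day window and may be done by home visit or telephone. This stands, though no rate is given.
- **The dates may be incomplete.** Footnote q asks for them in the same instruction as the score. The SAP does not say they are filled in for a missed assessment, or that oxygen use at another hospital is captured. A reader might infer that the true Day 14 category is always known; the SAP supports only that the binary status may be derivable where records are complete.
- **A safeguard exists.** Counting missing values as progression tests the error in which LOCF hides a progression, and the missing-value table shows how many patients are involved. But that analysis ignores the same dates and leaves the main analysis unchanged.
- **LOCF is prespecified and identical in both arms.** True, but that does not make it preferable to recorded status.

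**Conclusion.** The point holds for the binary primary outcome on Day 14. The SAP carries an earlier score forward without checking dated records that it requires and that, where complete, settle whether the patient had progressed. It matters most after discharge.

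The expected size is modest. Each miscoded patient moves an arm's rate by 1.25 or 2.5 points. At m = 2% the difference stays within 0.24 points of the planned 20. The fall in power to 78.2% needs about 12 patients with isolated gaps and 30% of the carried values wrong, and both figures are assumptions.

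Two stronger readings are not supported. One is that LOCF would shift the result by 5 points, a quarter of the planned difference. That requires two errors in Arm B (2/40), in the same direction, with nothing offsetting in Arm A. A hidden progression in Arm B would shrink the apparent benefit, while one in Arm A would enlarge it, so the direction is not fixed. The other is that the same fault affects Day 28: Section 7.2 contains no LOCF rule.

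**What to change.** In Sections 7.1 and 10.1, replace the LOCF sentence with an ordered rule:

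1. If the Day 14 score is missing, derive progression status (1-4 versus 5-8) from the recorded dates of death, hospitalization and discharge, ventilation/ECMO, and high-flow and supplemental oxygen. Combine hospital status with respiratory support, and apply the Section 5.2 note on oxygen use before COVID-19. State what counts as a complete record, and treat a derived status as observed.
2. Put only patients whose status remains undetermined into the multiple imputation already planned.
3. Keep LOCF as a sensitivity analysis beside the one that counts missing values as progression.
4. In the planned missing-value table, show by arm how many values were derived and how many imputed.

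The cost is one derivation rule and some programming, with no new data. The imputation model must also accept a gap followed by a later observation, for which the Day 28 score can serve as a predictor. The benefit is limited to patients whose component dates are complete. The rule should be fixed before unblinding.
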